16.4 Missing, unused & spurious data

Our primary outcome will be analysed as a time-to-event variable, with missing observations censored at the final time at which data were available.

Further detail is provided in the ENCEPH-IG Statistical Analysis Plan (SAP).

16.5 Procedures for reporting deviation(s) from the original SAP

These will be submitted as substantial amendments where applicable and recorded in subsequent versions of the protocol and SAP.

16.6 Termination of the trial

Progression criteria for the internal pilot phase are described in section 14. There is potential for the study to terminate early if our funder assesses the trial as not being feasible following an assessment of progress against our targets at the end of the internal pilot with input from our TSC and IDMC.

16.7 Inclusion in analysis

This is a trial of a rare disease and is likely to be the definitive trial of IVIG in autoimmune encephalitis. While this trial was funded to determine the efficacy of early IVIG on recovery in patients with autoimmune encephalitis, there are several factors which may limit the ability to do so:

- A pragmatic definition of autoimmune encephalitis upon trial entry;
- The ability of treating clinicians to provide therapeutics to participants which may confer similar benefits as IVIG, and treatment decisions likely to be based on evidence of clinical improvement following randomisation (i.e. the primary outcome);
- Theoretical access to therapeutic IVIG in both arms, which may be given under similar conditions to the above.

For these reasons, it is necessary to consider several analysis populations, reflecting both the explanatory and pragmatic aspects of our study design:

- Intention to treat (Effectiveness) analysis population all randomised participants, regardless
 of treatments received. This is a typical definition of an intention to treat population and will be
 used to assess the effectiveness of the treatment strategy of early IVIG.
- Efficacy analysis population participants who receive the treatment to which they were allocated. This reflects a typical definition of a per-protocol population. This will be used to assess the efficacy of early IVIG.

17 Analysis

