10.2 Lost to Follow Up

Sites will contact patients for each visit in accordance with the procedure outlined in section 13.2. If patients are not able to be contacted after three missed regular (fortnightly or monthly) GOSE assessment, a letter will be sent out to the participant asking them to get in contact with the trial team. Participants will not be contacted again until the 3 month, 12 month, or annual follow up occurs. Sites will record all details regarding attempts to contact the participant on the appropriate CRF. To minimise missing data, participants will be able to complete the primary outcome online or over the phone. In addition, contact details for participant's study partner will be collected and they will be able to complete the primary outcome on behalf of the participant. All data from participants will be collected regardless of their adherence to the protocol.

11 Trial Intervention

Patients will receive IVIG (2g/kg over 5 days) or placebo (Saline solution).

IVIG is a preparation of antibodies made from blood donations. It is licensed for use in patients with primary and secondary immunodeficiencies and for certain neurological conditions, such as Guillain-Barré syndrome. IVIG is given to many patients with autoimmune encephalitis. However, its efficacy is not known, and being a blood product, it carries risk of side effects.

We choose 2g/kg IVIG over 5 days (0.4g/kg/day for 5 days) because it is the dosing regimen most commonly used in neuro-inflammatory conditions, including in Guillain-Barré syndrome, and is the dose used in the pilot study of IVIG in encephalitis (Rayamajhi et al., 2015).

All patients will also receive methylprednisolone 1g daily intravenously for 5 days, followed by 1mg/kg (up to 60mg daily maximum) oral prednisolone daily for two weeks, followed by a taper regime (see section 11.4 for full dosing schedule).

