17.1 Main analysis

The primary analysis will be based on the intention to treat analysis population and will use Cox regression to estimate the difference in time from randomisation to recovery (defined as two consecutive GOSE scores ≥5 according to the assessment schedule defined in Section 5.3) between the IVIG and placebo arms. A two-level frailty model will be used to account for any clustering of participants within sites. Results will be reported as hazard ratios, with associated 95% confidence intervals and p-values. Considering the efficacy analysis population, we will estimate the efficacy of early IVIG on time

to recovery using inverse probability-of-censoring weighting methods (Dodd, Williamson, & White, 2017). This will account for instances of treatment switching and the use of further immunotherapy (IVIG, steroids plasma exchange, or other), while importantly maintaining a comparison of groups as randomised. Our weights will consider both baseline and time-varying covariates that predict treatment changes. We suspect that the decision to initiate further immunotherapy will be because of a perceived lack of response to treatment or because of a positive anti-neuronal antibody result. We will therefore ensure that sufficient data are collected to capture these decisions.

Secondary outcomes will be analysed by fitting a two-level regression model accounting for participants within sites (linear, logistic, Poisson, or Cox proportional hazards model), as appropriate. For both our effectiveness and efficacy populations, we will consider the impact of missing data on the conclusions drawn on our analyses. Plausible missing data mechanisms will be considered, and approaches allowing us to arrive at treatment effect estimates which are valid under Missing At Random (e.g. multiple imputation) and Missing Not At Random (e.g. selection or pattern mixture models) will be considered as sensitivity analyses.

A fully detailed statistical analysis plan will be written and signed-off prior to database lock. All data manipulation prior to analysis will be undertaken by the main trial statistician, who will remain blind to treatment arm until the point of analysis. The study results will be reported in accordance with the Consolidated Standards of Reporting Trials (CONSORT) 2010 statement.

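### The efficacy population is a per-protocol subset, but the weighted analysis run in it is said to compare the groups as randomised; both cannot hold

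*Protocol*

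**What the plan says.** Protocol section 16.7 sets up two analysis populations. The intention-to-treat population is "all randomised participants, regardless" of what they received. The efficacy population is "participants who receive the treatment to which they were allocated. This reflects a typical definition of a per-protocol population", and it is to be used to assess the efficacy of early IVIG.

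Section 17.1 assigns the analyses. "The primary analysis will be based on the intention to treat analysis population". For the second estimate it says: "Considering the efficacy analysis population, we will estimate the efficacy of early IVIG on time" to recovery, by inverse probability-of-censoring weighting. Of that method it says "This will account for instances of treatment switching and the use of further immunotherapy", and that it does this "while importantly maintaining a comparison of groups as randomised". The weights are to use baseline and time-varying predictors of treatment change.

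Two further statements matter. Among the factors that may limit the trial's ability to determine efficacy, section 16.7 lists "treatment decisions likely to be based on evidence of clinical improvement following randomisation (i.e. the primary outcome". Section 10.2 says: "All data from participants will be collected regardless of their adherence to the protocol".

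**The concern.** IPCW keeps a randomised comparison because it begins with everyone randomised. Each participant contributes until the first departure from allocated treatment and is then artificially censored. Similar participants who have not departed are weighted up to stand in for those censored. A per-protocol subset works the other way: anyone who departs is removed from time zero, including the follow-up before the departure.

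If section 16.7 is applied as written, the weighting in section 17.1 has no switchers to act on and the comparison is not of groups as randomised. If switchers are kept until they switch, the population is not the one that section 16.7 defines. Two analysts could each claim to follow the protocol and report different efficacy hazard ratios.

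The selection is unlikely to be harmless, because the protocol expects treatment decisions to depend on clinical course. Those who receive rescue are, by construction, people who had not recovered by the time of rescue. Section 16.7 says the trial was funded to determine the efficacy of early IVIG, and this is the only estimate labelled as doing so.

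**Working it through.** **Which analysis the sample size serves.** Section 16.3 gives a two-sided alpha of 0.05, 85% power, a hazard ratio (HR) of 1.43, 20% of placebo participants unrecovered at 12 months and 5% drop-out.

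- Freedman events: (1.960 + 1.036)² × (2.43/0.43)² = 287.
- Event probability: placebo 0.80; IVIG 1 − 0.20^1.43 = 0.90; mean 0.85.
- 287/0.85 = 338, and 338/0.95 = 356.

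This matches the stated 356. It sizes the intention-to-treat analysis, so the present point does not change it. The protocol gives no figure for the efficacy analysis.

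**The two sections side by side.**

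| | Section 16.7 | Section 17.1 |
|---|---|---|
| Who is included | Those who received their allocated treatment | The same population, by name |
| Treatment switchers | Excluded if switching means the allocated treatment was not received | Handled by censoring and weighting, so must be present |
| Comparison | Per-protocol | As randomised |

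**How exclusion biases the HR.** This is an illustration; the rescue timing and rates are assumptions.

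- The placebo hazard is ln 2/87 per day to day 87, then ln 2.5/278 per day to day 365. This gives the protocol's median of 87 days and 0.5/2.5 = 20% unrecovered at 12 months.
- The true HR is 1.43. Rescue occurs at day 28 among those unrecovered and has no effect of its own. Rescued participants are dropped from the start.
- Placebo unrecovered at day 28: 0.5^(28/87) = 0.80. Dropping 30% of them removes 0.30 × 0.80 = 24% of the placebo arm and leaves 76%.
- All recoveries before day 28 stay in, over a smaller denominator. The placebo hazard is therefore inflated by 1/0.76 at day 0, rising to 1/0.70 just before day 28. The apparent HR is 1.43 × 0.76 = 1.09 at day 0 and 1.43 × 0.70 = 1.00 just before day 28. After day 28 it is 1.43 again.

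Cox fits to large simulated samples under this model average over those periods:

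| Excluded among those unrecovered at day 28 (placebo/IVIG) | Subset HR, true 1.43 | Subset HR, true 1.00 |
|---|---|---|
| 10%/0% | about 1.37 to 1.39 | about 0.97 to 0.98 |
| 30%/0% | about 1.29 | about 0.92 |
| 50%/0% | about 1.16 | about 0.84 |
| 30%/30% | about 1.41 | about 1.0 |

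**Second model, with rescue more likely in worse prognosis.** Assumptions: 400,000 simulated participants, log-normal frailty with SD 1, placebo median 87 days with 16% unrecovered at 12 months, switching at day 21, no effect of switching, true switching probabilities used for the weights. Percentages here are of the whole arm.

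| Switching (placebo/IVIG) | Null: subset | Null: IPCW, all randomised | Benefit (marginal HR 1.27): subset | Benefit: IPCW, all randomised |
|---|---|---|---|---|
| 5%/0% | 0.98 | 1.00 | 1.24 | 1.27 |
| 10%/0% | 0.95 | 1.00 | 1.20 | 1.27 |
| 20%/10% | 0.94 | 1.00 | 1.19 | 1.27 |
| 30%/10% | 0.85 | 1.00 | 1.08 | 1.27 |
| 30%/30% | 1.01 | 1.01 | 1.31 | 1.28 |

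Excluding only non-starters (10%, related to severity but not to arm) leaves the HR almost unchanged: 1.00 to 1.00 under the null, 1.27 to 1.28 under benefit.

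**The case against.** The strongest reply is that a coherent reading exists. Allocated treatment can be taken to mean the blinded five-day course, with later immunotherapy as something separate; section 11.1 and its treatment schedule list further treatment in its own column. A placebo participant rescued on day 28 would then have received the allocated treatment. Section 16.7 would drop only those who did not receive the blinded course, and section 17.1 would censor and weight later departures. Naming IPCW makes little sense unless switchers are in the data. On this reading the bias is small.

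That reading is possible, but section 16.7 does not state it, and it labels the population per-protocol. Even so read, removing participants after randomisation means the groups are not strictly as randomised.

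A second reply is that the trial is double-blind. With an intact blind and no true effect, rescue rates should not differ by arm, and equal exclusion gives almost no bias. This stands as far as it goes: the null figures below 1 need exclusion that differs by arm. The definition can produce that without any unblinding. A placebo participant given rescue IVIG has received the other arm's treatment, whereas an IVIG participant given more IVIG has still received the allocated one. If 30% of those unrecovered in both arms had rescue IVIG and only the placebo participants were dropped, the 30%/0% row of the first table would apply.

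A third reply is that the documents support no particular rescue rate, and that sections 11.1 and 11.9 place IVIG after other options have been considered. This is correct, and 50% is an extreme input. The pilot contamination measure in section 14.1 covers only the first 14 days, so it does not bound later use either.

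Finally, details of weight models and censoring events can be left to the statistical analysis plan. The population and the claim made for it are fixed in the protocol, however, and those are what conflict.

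**Conclusion.** The point holds as an internal contradiction: the population defined in section 16.7 defeats the property that section 17.1 claims for the analysis. It concerns the secondary efficacy estimate only.

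The size of any bias is not fixed by the documents. Under the assumptions shown, exclusion mainly from placebo takes a true HR of 1.43 to about 1.29 (30%/0%) or 1.16 (50%/0%), and a null to about 0.92 or 0.84. Exclusion equal by arm, or of non-starters only, gives almost none. IPCW on all randomised participants recovers the true value in these simulations, which used the correct weights.

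A reader might infer three stronger things that the material does not support:

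- That the main result is compromised. It is not: the primary analysis uses all randomised participants, and the sample size stands.
- That a real benefit could appear as harm. Every benefit scenario examined stays above 1, so dilution is shown and reversal is not.
- That the bias must run against IVIG. With equal 30%/30% switching in the frailty model the HR moved slightly upwards, from 1.27 to 1.31.

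**What to change.** In section 16.7, replace the per-protocol definition with an efficacy analysis that:

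- starts from all randomised participants at randomisation;
- censors each artificially at the first departure from allocated treatment, meaning allocated course not received, treatment switching, or further immunotherapy of the kinds listed in section 17.1;
- weights the remaining person-time by the inverse probability of being uncensored, from baseline and time-varying predictors of treatment change.

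The antibody result is an obvious predictor, since section 17.1 expects it to prompt further treatment. The GOSE is another. Section 17.1 does not name it as a weight covariate, but section 13.1 already collects it fortnightly and then monthly until recovery. Align section 17.1 and the statistical analysis plan with this before unblinding. If a per-protocol subset analysis is kept as well, label it as not preserving randomisation.

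The cost is wording. Section 10.2 already keeps data on non-adherers, so no new data are needed, and the sample size does not change. The price in the analysis is some loss of precision from weighting, and reliance on a correctly specified weight model.

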17.1 Main analysis

The primary analysis will be based on the intention to treat analysis population and will use Cox regression to estimate the difference in time from randomisation to recovery (defined as two consecutive GOSE scores ≥5 according to the assessment schedule defined in Section 5.3) between the IVIG and placebo arms. A two-level frailty model will be used to account for any clustering of participants within sites. Results will be reported as hazard ratios, with associated 95% confidence intervals and p-values. Considering the efficacy analysis population, we will estimate the efficacy of early IVIG on time

to recovery using inverse probability-of-censoring weighting methods (Dodd, Williamson, & White, 2017). This will account for instances of treatment switching and the use of further immunotherapy (IVIG, steroids plasma exchange, or other), while importantly maintaining a comparison of groups as randomised. Our weights will consider both baseline and time-varying covariates that predict treatment changes. We suspect that the decision to initiate further immunotherapy will be because of a perceived lack of response to treatment or because of a positive anti-neuronal antibody result. We will therefore ensure that sufficient data are collected to capture these decisions.

Secondary outcomes will be analysed by fitting a two-level regression model accounting for participants within sites (linear, logistic, Poisson, or Cox proportional hazards model), as appropriate. For both our effectiveness and efficacy populations, we will consider the impact of missing data on the conclusions drawn on our analyses. Plausible missing data mechanisms will be considered, and approaches allowing us to arrive at treatment effect estimates which are valid under Missing At Random (e.g. multiple imputation) and Missing Not At Random (e.g. selection or pattern mixture models) will be considered as sensitivity analyses.

A fully detailed statistical analysis plan will be written and signed-off prior to database lock. All data manipulation prior to analysis will be undertaken by the main trial statistician, who will remain blind to treatment arm until the point of analysis. The study results will be reported in accordance with the Consolidated Standards of Reporting Trials (CONSORT) 2010 statement.

17.1.1 Sub-group analysis

Subgroup analyses will explore differential intervention effects on the primary outcome by age, disease severity on admission, and antibody status. The statistical model used for the primary analysis will be extended to include the subgroup and a trial arm x subgroup interaction term.

18 Data Management

Source Data is defined as "All information in original records and certified copies of original records of clinical findings, observations or other activities in a clinical trial necessary for the reconstruction and evaluation of the trial. Source data are contained in source documents." There is only one set of source data at any time for any data element, as defined in site source data agreement.

The source data for ENCEPH-IG trial will be from a variety of sources (see figure 5). Data will be collected using an electronic system (eCRF system) with paper CRF back up. There will also be data collected from participants' medical notes and patient reported questionnaires. Training for completion of study CRFs will be provided to the appropriate trial staff prior to trial commencement at site initiation.

Figure 5 Source Data

Trial data	Source Data					
	CRF	Participant medical notes	Electronic System	Pharmacy File	Questionnaire	SAE form
Medical History		X				
Concomitant Medications		Х				
Adverse events			Х			х
Demographics			Х			
Physical examination		Х				
Vital signs		Х				
Eligibility assessment			Х			
MRI/ CT Scan		Х				
Compliance			Х			
Glasgow Outcome Scale Extended			Χ			
Use of further immunotherapy		Х				
Clinical assessment		Х				
EuroQoL Five Dimension Scale			X			
European Brain Injury Questionnaire			Х			
Modified Rankin Scale			Х			
Liverpool Outcome Score			Х			
Barthel Index			Х			
Addenbrooke's Cognitive Examination III					Х	

Trial data	Source Data					
	CRF	Participant medical notes	Electronic System	Pharmacy File	Questionnaire	SAE form
Verbal Memory Test					Х	
Wechsler Memory Scale Version IV					Х	
WAIS Version IV: Processing Speed Index					Х	
WAIS Version IV: Working Memory Index					Х	
Confrontational Naming task (from Neuropsychology Assessment Battery)					Х	
Trial Making Test Part A and B					Х	
Premorbid Cognitive Ability (TOPF)					Х	
Beck Depression Inventory			Х			
Beck Anxiety Inventory			Х			
Perceived Deficits Questionnaire						
Physician's Withdrawal Checklist			Х			

18.1 Completion of CRFs

All assessments and data collection will be completed using web-based CRFs, except for the SAE from and several of the neuropsychological assessments. This is a secure encrypted system accessed by username and password and complies with General Data Protection Regulation 2016. In the event that the web-based system is not accessible, paper CRFs will be used to record data. The data will then be inputted by local site staff into the web-based system once it is accessible. A full Data Management Plan will accompany this protocol and will be stored in the TMF.

18.1.1 Electronic CRFs

It is intended to develop data recording for this trial as a web-based system. This is a secure encrypted system and complies with the General Data Protection Regulation 2016 standards. The system can accessed by an institutional password supplied to investigators upon completion of all processes

required prior to opening. Participants and study partners will be sent a unique link to be able to complete the GOSE safely and securely online. All electronic CRFs will be developed and tested in accordance with the relevant Centre for Trials Research SOPs. Electronic CRFs will contain validations and checks to maintain data quality.

18.1.2 Paper CRFs

A select number of forms, including the SAE form and those administered as part of battery of the neuropsychology and cognitive tests, will be completed on paper first and the finalised scores entered into the electronic database.

For all other forms, if the electronic database is not available, paper CRFs will be used and data will be entered on to the database at a later point (within a week) by local site staff. In accordance with the principles of GCP, the PI is responsible for ensuring accuracy, completeness, legibility and timeliness of the data reported to the CTR in the CRFs.

If missing or questionable data are identified, a data query will be raised on a data clarification form. The data clarification form will be sent to the relevant site. The site shall be requested to respond to the data query on the data clarification form. The CRF pages should not be altered. All answered data queries and corrections should be signed off and dated by a delegated member of staff at the relevant site. The completed data clarification form should be returned to the CTR and a copy retained at the site along with the participant's CRFs.

The CTR will send reminders for any overdue data. It is the site's responsibility to submit complete and accurate data in timely manner. Further details of data management procedures will be specified in the Data Management Plan.

19 Exploratory sub-studies

The mechanisms of action of IVIG are incompletely understood.

Glycosylation of host immunoglobulin (IgG Fc region) is thought to play a critical role. Through targeted experiments, we will examine the host response in autoimmune encephalitis, and test two hypotheses to explain IVIG's therapeutic effects.

1. We hypothesise that patients with autoimmune encephalitis have aberrant IgG Fc glycosylation, and that IVIG modulates this (Czajkowsky et al., 2015).

2. As a result of the above, we hypothesise that IVIG will reduce levels of anti-neuronal antibodies, as well as down-regulating pro-inflammatory host pathways, and that this will correlate with clinical improvement.

IgG Fc glycosylation (serum and CSF) will be measured at baseline and 3 months among participants. We will examine whether glycosylation differs among participants treated with IVIG compared to placebo (adjusted for baseline glycosylation). We will also examine whether glycosylation titres relate to the presence of anti-neuronal antibodies , host inflammatory markers (measured at baseline) or clinical outcome.

